## **7.2.4 Dose Modification of Ibrutinib**

### **7.2.4.1 Dose modifications for adverse events:**

Interrupt ibrutinib therapy for any Grade 3 or greater non-hematological, Grade 3 or greater neutropenia with infection or fever, or Grade 4 hematological toxicities. Once the symptoms of the toxicity have resolved to Grade 1 or baseline (recovery), ibrutinib therapy may be reinitiated at the starting dose. If the toxicity reoccurs, reduce dose by one capsule (140 mg per day). A second reduction of dose by 140 mg may be considered as needed. If these toxicities persist or recur following two dose reductions, discontinue ibrutinib (refer to Table 3 below).

**Table 3: Ibrutinib Dose Modifications**

Adverse Events Occurrence	Action to be Taken
First	Withhold ibrutinib until recovery to Grade $\leq 1$ or baseline; may restart at original dose level
Second	Withhold ibrutinib until recovery to Grade $\leq 1$ or baseline; may restart at 1 dose level lower (ie, 420 mg/day)
Third	Withhold ibrutinib until recovery to Grade $\leq 1$ or baseline; may restart at 1 dose level lower (ie, 280 mg/day)
Fourth	Discontinue ibrutinib

\*if Ibrutinib is discontinued for toxicity, subject will end the Treatment Phase of the study.

\*Ibrutinib dosing at 420 mg could be administered on an individual patient basis as per Investigator discretion dose modifications are required. Dose changes must be recorded in the Dose Administration eCRF.

#### **7.2.4.2 Dose modifications for use with CYP3A inhibitors**

**Table 4: Recommended Ibrutinib Dose Modifications for use with CYP3A Inhibitors**

Patient Population	Coadministered Drug	Recommended Ibrutinib Dose
B-Cell Malignancies	
 
Moderate CYP3A inhibitor
 
	280 mg once daily Modify dose as recommended.
	
 
Voriconazole 200 mg twice daily
 
Posaconazole suspension 100 mg once daily, 100 mg twice daily, or 200 mg twice daily
 
	140 mg once daily Modify dose as recommended.

	
 
• Posaconazole suspension 200 mg three times daily or 400 mg twice daily
 
• Posaconazole IV injection 300 mg once daily
 
• Posaconazole delayed-release tablets 300 mg once daily
 
	70 mg once daily Interrupt dose as recommended.
	
 
• Other strong CYP3A inhibitors
 
	Avoid concomitant use. If these inhibitors will be used short-term (such as anti-infectives for seven days or less), interrupt ibrutinib.

Avoid co-administration with strong or moderate CYP3A inhibitors and consider alternative agents with less CYP3A inhibition.

Concomitant use of strong CYP3A inhibitors which would be taken chronically (e.g., ritonavir, indinavir, nelfinavir, saquinavir, boceprevir, telaprevir, nefazodone) is not recommended. For short-term use (treatment for 7 days or less) of strong CYP3A inhibitors (e.g., antifungals and antibiotics) consider interrupting ibrutinib therapy until the CYP3A inhibitor is no longer needed.

Reduce ibrutinib dose to 280 mg if a moderate CYP3A inhibitor must be used (e.g., fluconazole, darunavir, erythromycin, diltiazem, atazanavir, aprepitant, amprenavir, fosamprenavir, crizotinib, imatinib, verapamil, and ciprofloxacin).

Patients taking concomitant strong or moderate CYP3A inhibitors should be monitored more closely for signs of ibrutinib toxicity.

#### **7.2.4.3 Dose modifications for use in hepatic impairment**

For patients with mild liver impairment (Child-Pugh class A), the recommended dose is 140 mg daily (one capsule). Avoid the use of ibrutinib in patients with moderate or severe hepatic impairment (Child-Pugh classes B and C).

#### **7.2.5 Prohibitions and Restrictions**

The following guidance should be applied during the perioperative period for subjects who require surgical intervention or an invasive procedure while receiving ibrutinib:

- For any planned surgery or invasive procedure requiring sutures or staples for closure, ibrutinib should be held at least 7 days prior to the intervention and should be held at least 7 days after the procedure, and restarted at the discretion of the investigator when the surgical site is reasonably healed without serosanguinous drainage or the need for drainage tubes.

- For planned minor procedures (such as a central line placement, needle biopsy, thoracentesis, or paracentesis) ibrutinib should be held for at least 3 days prior to the procedure and should not be restarted for at least 3 days after the procedure. For bone marrow biopsies that are performed while the subject is on ibrutinib, it is not necessary to hold ibrutinib for these procedures.
- For emergency procedures, ibrutinib should be held after the procedure until the surgical site is reasonably healed, for at least 7 days after the urgent surgical procedure, or at the discretion of the investigator.

#### **7.2.6 Tumor Lysis Syndrome**

Tumor lysis syndrome has been reported with ibrutinib therapy. Monitor patients closely and take appropriate precautions in patients at risk for tumor lysis syndrome (e.g. high tumor burden). Additional information regarding TLS prophylaxis and management can be found in section 7.1.3

### **7.3 POTENTIAL FOR DRUG-DRUG INTERACTIONS**

Based on preliminary data from the combination studies of ibrutinib and venetoclax, venetoclax exposure (area under the concentration-time curve [AUC]) at 400 mg QD appears to be approximately 1.6-fold higher with 420 mg ibrutinib (chronic lymphocytic leukemia [CLL], N=32) and approximately 2-fold higher with 560 mg ibrutinib (mantle cell lymphoma [MCL], N=6) compared with venetoclax single agent exposure.

Within the same dataset, ibrutinib exposures when dosed in combination with venetoclax were comparable to those observed at the respective therapeutic dose levels of ibrutinib single agent.

To date, no new safety signals have been identified in the ongoing combination studies.

Patients will be closely monitored for signs of toxicity.

### **7.4 RITUXIMAB**

#### **7.4.1 Rituximab Administration**

Investigators should refer to the package inserts for the storage and handling, and detailed instructions on the administration of rituximab. (MabThera (rituximab); Rituxan [prescribing information]) It is strongly recommended that premedication guidelines are also followed per rituximab package insert. Rituximab is administered IV, per institutional standards, weekly X 4 (Cycle 1); once on Day 1 of cycles 2-6 only, then every other cycle until Cycle 24 (total 18 doses of Rituxan from C1D1) Commercially available rituximab IV will be used.

### **7.5 DRUG COMPLIANCE**

Drug compliance will be monitored by recording dose administration by subjects in a diary. The diary will be handed out with each new cycle and must be returned at the end of each cycle with the bottles of ibrutinib and venetoclax.

## **7.6 DISPOSAL, DESTRUCTION, AND ACCOUNTABILITY**

Drug destruction and accountability will be maintained by pharmacy. Bottles of ibrutinib and venetoclax will be returned to pharmacy and accounted for and destroyed as per institutional policy.

## **8. CONCOMITANT MEDICATIONS/PROCEDURES**

### **8.1 CONCOMITANT MEDICATIONS**

#### **8.1.1 Permitted Concomitant Medications**

Supportive medications in accordance with standard practice (such as for emesis, diarrhea, etc.) are permitted. Erythropoietic growth factors (eg, erythropoietin) and hematopoietic growth factors are allowed per institutional policy and in accordance with the ASCO guidelines (Smith 2006).

Transfusional support (packed red blood cells and platelets) may be given in accordance with institutional policy. If platelet transfusion is required during the DLT period, this will meet criteria of a DLT.

Short courses ( $\leq 14$  days) of steroid treatment for non-cancer-related medical reasons (eg, joint inflammation, asthma exacerbation, rash, antiemetic use and infusion reactions) at doses that do not exceed 100mg per day of prednisone or equivalent are permitted.

Prophylaxis for hepatitis is permitted as per local guidelines provided no contraindicated antiviral medications are used.

#### **8.1.2 Medications to be used with Caution**

##### **8.1.2.1 CYP3A4/5 Inhibiting/Inducing Drugs**

In healthy volunteers, co-administration of ketoconazole, a strong CYP3A inhibitor, increased  $C_{max}$  and AUC of ibrutinib by 29- and 24-fold, respectively. The highest ibrutinib dose evaluated in clinical trials was 12.5 mg/kg (actual doses of 840 – 1400 mg) given for 28 days with single dose AUC values of  $1445 \pm 869 \text{ ng} \cdot \text{hr}/\text{mL}$  which is approximately 50% greater than steady state exposures seen at the highest indicated dose (560 mg).

Avoid concomitant administration of ibrutinib with strong or moderate inhibitors of CYP3A. For strong CYP3A inhibitors used short-term (e.g., antifungals and antibiotics for 7 days or less, e.g.,

ketoconazole, itraconazole, voriconazole, posaconazole, clarithromycin, telithromycin) consider interrupting ibrutinib therapy during the duration of inhibitor use.

Avoid strong CYP3A inhibitors that are needed chronically. If a moderate CYP3A inhibitor must be used, reduce the ibrutinib dose. Patients taking concomitant strong or moderate CYP3A4 inhibitors should be monitored more closely for signs of ibrutinib toxicity. Avoid grapefruit and Seville oranges during ibrutinib treatment, as these contain moderate inhibitors of CYP3A.

Administration of ibrutinib with rifampin, a strong CYP3A inducer, decreased ibrutinib  $C_{max}$  and AUC by approximately 13- and 10-fold, respectively.

Avoid concomitant use of strong CYP3A inducers (e.g., carbamazepine, rifampin, phenytoin and St. John's Wort). Consider alternative agents with less CYP3A induction.

Please refer to USPI and IB for more information.

### **8.1.2.2      Drugs that may Have Their Plasma Concentrations Altered by Ibrutinib**

In vitro studies indicated that ibrutinib is not a substrate of P-glycoprotein (P-gp), but is a mild inhibitor (with an IC50 of 2.15  $\mu$ g/mL). Ibrutinib is not expected to have systemic drug-drug interactions with P-gp substrates. However, it cannot be excluded that ibrutinib could inhibit intestinal P-gp after a therapeutic dose. Currently, no clinical data is available; therefore, coadministration of narrow therapeutic index P-gp substrates (eg, digoxin) with ibrutinib may increase the substrate's blood concentration and should be used with caution and subjects should be monitored closely for toxicity.

### **8.1.2.3      Concomitant Use of QT Prolonging Agents**

Any medications known to cause QT prolongation should be used with caution; periodic monitoring with electrocardiograms and electrolytes should be considered.

### **8.1.2.4      Concomitant Use of Antiplatelet Agents and Anticoagulants**

Warfarin or vitamin K antagonists should not be administered concomitantly with ibrutinib. Supplements such as fish oil and vitamin E preparations should be avoided. Use ibrutinib with caution in subjects requiring other anticoagulants or medications that inhibit platelet function. Subjects with congenital bleeding diathesis have not been studied.

Fatal bleeding events have occurred in patients treated with ibrutinib. Grade 3 or higher bleeding events (subdural hematoma, gastrointestinal bleeding, hematuria and post procedural hemorrhage) have occurred in up to 6% of patients. Bleeding events of any grade, including bruising and petechiae, occurred in approximately half of patients treated with ibrutinib.

The mechanism for the bleeding events is not well understood.

Ibrutinib may increase the risk of hemorrhage in patients receiving antiplatelet or anticoagulant therapies.

Consider the benefit-risk of withholding ibrutinib for at least 3 to 7 days pre and postsurgery depending upon the type of surgery and the risk of bleeding

### **8.1.3        Prohibited Concomitant Medications**

Any chemotherapy, anticancer immunotherapy (besides rituximab), experimental therapy (besides venetoclax) or radiotherapy is prohibited while the subject is receiving study treatment.

Corticosteroids for the treatment of the underlying disease is prohibited. Corticosteroids for the treatment of non-cancer related reasons for longer than 14 days and/or at doses >100mg of prednisone or its equivalent are prohibited. See [Section 8.1.2](#) for permitted uses.

Erythropoietic and hematopoietic growth factors are also prohibited during the Phase 1b DLT assessment period. See [Section 8.1.2](#) for permitted use.

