#### Hematologic:

- Grade 3 neutropenia (ANC <1,000/mm^3) that does not resolve to  $\leq$  Grade 2 within 3 weeks with the use of growth factor

- Grade 4 neutropenia (ANC <500/mm^3)
- Febrile neutropenia (ANC <1,000/mm^3 with a fever  $\geq 38.3^{\circ}\text{C}$ )
- Grade 4 thrombocytopenia (<25,000/mm^3) that persists for  $\geq 7$  days, despite holding treatment
- Grade 3 thrombocytopenia associated with Grade  $\geq 2$  bleeding or requiring RBC or platelet Transfusions

Non-Hematologic:

- Any Grade 3 or higher non-hematologic adverse event where relationship to study drug(s) cannot be ruled out (Note: excludes rituximab infusion reactions)
- Grade  $\geq 3$  nausea, vomiting, or diarrhea uncontrolled by maximal supportive care and persisting greater than 7 days
- Grade 3 fatigue persisting for greater than 7 days
- Treatment delay of any drug greater than 7 days for toxicity

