### **7.1.2 Concomitant Therapies**

Concomitant therapy includes any prescription medications or over-the-counter preparations used by a patient between the 14 days preceding the study entry evaluation and the early study treatment termination visit/study treatment completion visit.

Patients who use oral contraceptives, hormone-replacement therapy, or other maintenance therapy should continue their use for the duration of the study for at least 3 months after the last dose of venetoclax and 12 months after the last dose of Rituximab.

Necessary supportive measures for optimal medical care will be given throughout the study according to institutional standards, including the use of growth factors (e.g., erythropoietin) if clinically indicated. Granulocyte colony-stimulating factor (G-CSF) may be administered as primary prophylaxis in each cycle of therapy, per the American Society of Clinical Oncology guidelines (Smith et al. 2006) or each site's institutional standards.

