**Table 1 Dose Modifications for Hematologic Toxicity Venetoclax Monotherapy**

Hematologic Toxicity	
Event(s)	Dose Delay or Modification
Grade 3 or 4 neutropenia, without infection or fever, and/or Grade 3 or 4 thrombocytopenia, first episode	

• Hold venetoclax.

• When counts recover to <math>\leq</math> Grade 2, resume previous doses of venetoclax.

• Administer G-CSF or growth factors for neutropenia as indicated.

• If the patient was not previously receiving prophylactic G-CSF, initiate prophylactic G-CSF for neutropenia as indicated.

Grade 3 or 4 neutropenia with infection and/or fever, first episode	

• Begin anti-viral medication and hold venetoclax until fever and/or infection resolves.

• Administer G-CSF or growth factors for neutropenia as indicated.

• When counts recover to <math>\leq</math> Grade 2 and infection has been fully treated, resume previous doses of venetoclax.

• If the patient was not previously receiving prophylactic G-CSF, initiate prophylactic G-CSF for neutropenia as indicated.

Recurrent Grade 3 or 4 neutropenia with/without fever and infection despite G-CSF	

• Hold venetoclax for at least 7 days.

• Administer G-CSF or growth factors for neutropenia as indicated.

• When counts recover to <math>\leq</math> Grade 2 and/or platelets are <math>\geq 75 \times 10^9/L</math>, resume venetoclax at one dose level reduction (see Table 3).

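### Growth factors are banned in the DLT period (8.1.3), yet the Grade 3 neutropenia DLT is judged on recovery with growth factor, so that criterion cannot be applied as written in Cycle 1

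*Combined protocol and SAP*

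**What the plan says.** Five places in the combined protocol and SAP bear on growth-factor use in Cycle 1.

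- **8.1.3 (prohibited medications):** "Erythropoietic and hematopoietic growth factors are also prohibited during the Phase 1b DLT assessment period". It then refers the reader to 8.1.2 for permitted use.
- **5.1 and 12 (DLT lists, same wording in both):** Grade 3 neutropenia is a DLT only if it does not resolve to at most "Grade 2 within 3 weeks with the use of growth factor". Grade 4 neutropenia is a DLT at any duration, and febrile neutropenia is a DLT. A further bullet counts "Treatment delay of any drug greater than 7 days for toxicity".
- **7.1.2 (concomitant therapies):** G-CSF "may be administered as primary prophylaxis in each cycle of therapy", following a professional guideline or institutional standards.
- **7.1.4, Table 1 (hematologic toxicity):** for Grade 3 or 4 neutropenia, "Administer G-CSF or growth factors for neutropenia as indicated", and, after a first episode, "If the patient was not previously receiving prophylactic G-CSF, initiate prophylactic G-CSF for neutropenia as indicated". The table is titled for venetoclax monotherapy, but it is the only venetoclax hematologic table in the protocol.
- **8.1.1 (permitted medications):** "hematopoietic growth factors are allowed per institutional policy". This section sets a DLT-period rule for platelet transfusion but none for growth factors.

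The DLT period is Cycle 1 (28 days), with evaluation at Cycle 2 Day 1, Study Day 29 plus or minus 3 days (Section 5).

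**The concern.** The primary objective (2.1) is to find the MTD or recommended dose from DLT incidence. Under the 3+3 rule in Section 5, one or two events in three to six patients decide whether the dose goes up. A DLT criterion therefore has to mean the same thing for every patient in a cohort.

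Here it does not. The Grade 3 neutropenia bullet assumes a treatment that 8.1.3 forbids in the period in which the bullet is scored. If the ban is followed, the bullet tests unaided recovery in a patient with early onset, and recovery aided for part of the time in a patient with later onset. If 7.1.2 or Table 1 is followed instead, growth factor may be given throughout.

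There is also a problem at the bedside. An investigator with a neutropenic patient in Cycle 1 either gives the G-CSF that Table 1 calls for where indicated, and breaches 8.1.3, or withholds it and leaves the DLT bullet without its stated condition.

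**Working it through.** The plan gives no figure to reproduce: it states no operating characteristics for the 3+3 part. The check compares the texts and then counts days.

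**1. Can the rules be reconciled?**

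| Place | Force | Limited to, or excepting, the DLT period? |
|---|---|---|
| 8.1.3 | prohibition | yes, written for that period |
| 7.1.2 | permission, every cycle | no |
| 8.1.1 | permission | no |
| Table 1 | instruction, as indicated | no |
| 5.1 and 12, Grade 3 neutropenia | criterion that presupposes use | scored in that period |

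If a specific rule overrides a general one, 8.1.3 can prevail over the permissions in 7.1.2 and 8.1.1. The last row is not a permission. It is the scoring rule for the same period, and the ban removes its stated condition. No text says which rule prevails. Section 8.1.2, to which 8.1.3 points, covers CYP3A drugs, drugs whose levels ibrutinib may alter, QT-prolonging agents, and antiplatelet and anticoagulant drugs. It has no growth-factor rule.

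**2. How much of the 3-week clock falls under the ban?**

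Inputs: a 21-day clock (5.1, 12); weekly hematology in Cycle 1 (Section 6, Appendix 1); window end on Day 29, or Day 32 if the Cycle 2 Day 1 visit is 3 days late (5.1 takes the longer limit).

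Clock days under the ban = min(onset + 21, window end) − onset.

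| Grade 3 first seen | Window ends Day 29 | Window ends Day 32 |
|---|---|---|
| Day 8 | min(29, 29) − 8 = 21 | min(29, 32) − 8 = 21 |
| Day 15 | min(36, 29) − 15 = 14 | min(36, 32) − 15 = 17 |
| Day 22 | min(43, 29) − 22 = 7 | min(43, 32) − 22 = 10 |
| Day 29 | min(50, 29) − 29 = 0 | min(50, 32) − 29 = 3 |

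With a Day 29 end, the same bullet is judged with no growth factor available for anywhere from none to all of the 21 days, depending only on when the count fell.

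**3. What could this do to a dose decision? Illustration only.**

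The documents give no Cycle 1 rate of Grade 4 or febrile neutropenia and no G-CSF effect. Everything below is assumed: other DLTs b = 10%; Grade 4 or febrile neutropenia without G-CSF x = 5% to 15%; and a fraction r of those cases prevented by G-CSF.

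DLT rate p = 1 − (1 − b)(1 − x(1 − r)). Chance of clearing a level = (1 − p)³ + 3p(1 − p)⁵.

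| r | p at x = 5%, 15% | Clear the level | Gain in points |
|---|---|---|---|
| 0 | 0.145, 0.235 | 0.824, 0.632 | – |
| 25% | 0.134, 0.201 | 0.846, 0.706 | 2 to 7 |
| 50% | 0.1225, 0.1675 | 0.867, 0.778 | 4 to 15 |
| 75% | 0.111, 0.134 | 0.887, 0.846 | 6 to 21 |

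With b at 5% or 20% and r at 50%, the gain is 4 to 14 or 4 to 12 points. At r = 0 it is zero. The table fixes the direction, not the size.

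**The case against.** The strongest reply is that 8.1.3 is the only growth-factor sentence written for the DLT period, and that everything else is permissive: 7.1.2 says G-CSF may be given, 8.1.1 that it is allowed, and Table 1 qualifies it by indication. Withholding it in Cycle 1 breaches neither permission. The pointer also looks like a numbering slip, because 8.1.3 sends its corticosteroid sentence to 8.1.2 as well, although the steroid permission is in 8.1.1. Read with 8.1.1, the ban is a plain exception.

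Much of this stands. A reader might infer that 8.1.3 contradicts 7.1.2 and 8.1.1 beyond repair, or that Table 1 orders G-CSF for every neutropenic patient. The wording supports neither. But the reply does not reach the 3-week bullet, and it leaves Table 1 without an exception for Cycle 1.

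A second reply is that the bullet may rarely decide anything. If a Table 1 hold counts as a treatment delay, the 7-day delay bullet would score first. That is possible, but the protocol does not say whether a hold is a delay. Even then, growth-factor use would still affect how long the hold lasts. Grade 4 neutropenia is a DLT at any duration, so G-CSF given afterwards cannot undo it; there, only prophylaxis matters.

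A third reply is practical. Sections 3 and 6 describe a single center and 13.1 requires weekly investigator meetings, so one team could apply one rule. It could, but the protocol would not tell it which.

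**Conclusion.** The point holds. The ban in 8.1.3 and the Grade 3 neutropenia criterion in 5.1 and 12 cannot both be applied as written. With the window ending on Day 29, 21, 14 or 7 of the 21 clock days fall under the ban for onset seen on Day 8, 15 or 22. Sections 7.1.2 and Table 1 add to the uncertainty because neither excepts Cycle 1, and the pointer that should resolve it leads to no rule. Because this criterion feeds the primary endpoint, it needs correction and not just interpretation.

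The effect on DLT counts cannot be sized from the documents. Only its direction is clear: G-CSF would tend to lower neutropenia DLTs. A reader might infer from the illustration that the MTD is biased by a given number of points; that rests wholly on assumed rates and an assumed G-CSF effect.

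A reader might also infer support from the two venetoclax combination studies in 1.2.4 that had a G-CSF policy. They carry little weight, because both used a chemotherapy backbone, which this trial does not. In the bendamustine-rituximab study, G-CSF was encouraged because of backbone toxicity, and the DLT definition was revised in the same amendment. In the CHOP study, hematologic toxicity exceeded expectation despite mandatory G-CSF.

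Likewise, the mantle cell lymphoma experience cited in 12 reports more neutropenia but no increase in infection, and gives no Cycle 1 or Grade 4 rate.

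**What to change.** 1. Set one growth-factor rule for Cycle 1. One workable choice is no prophylactic growth factor in the DLT window, with therapeutic G-CSF allowed once Grade 3 or 4 neutropenia is documented. The clinical choice is the sponsor's.
2. Write that rule into 8.1.3, 7.1.2, 8.1.1 and Table 1.
3. Make the Grade 3 neutropenia bullet in 5.1 and 12 consistent with it. If the ban stays absolute, drop the growth-factor condition from the bullet. While doing so, state whether a Table 1 hold counts as a treatment delay and which bullet governs.
4. Change the growth-factor pointer in 8.1.3 from 8.1.2 to 8.1.1.
5. Report Cycle 1 G-CSF use, prophylactic and therapeutic, beside the DLT counts for each dose level.

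The cost is amendment wording, with no added patients or visits. If the 3-week test is kept as the governing test, a cohort decision may have to wait up to about three weeks for a clock that opens late in Cycle 1: onset on Day 22 runs to Day 43, and onset on Day 29 to Day 50.
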